### **11.2 AE Severity**

AEs are to be recorded on the AE page of the eCRF. Severity will be graded according to the following definitions as listed in Table 6 as well as the National Cancer Institute (NCI) Common Terminology Criteria for Adverse Events (CTCAE) Version 4.03. It should be pointed out that the term “severe” is a measure of intensity and that a severe AE is not necessarily serious.

When the intensity of an AE changes more than once a day, the maximum severity for the event should be listed. If the intensity changes over a number of days, these changes should be recorded separately (i.e., as having distinct onset dates).

**Table 6 Adverse Event Severity Grading**

Grade	Severity	Description
1	Mild	Transient or mild discomfort; no limitation in activity; no medical intervention or therapy required. The patient may be aware of the sign or symptom but tolerates it reasonably well.
2	Moderate	Mild to moderate limitation in activity, no or minimal medical intervention/therapy required.
3	Severe	Marked limitation in activity, medical intervention/therapy required, hospitalizations possible.
4	Life-threatening	The patient is at risk of death due to the adverse experience as it occurred. This does not refer to an experience that hypothetically might have caused death if it were more severe.
5	Death	Any adverse event where the outcome is death.

### 11.3 AE Relationship to Study Drug

The relationship of an AE to the study drug should be assessed using the following the guidelines in Table 7.

**Table 7 Adverse Event Relationship to Study Drug**

Relationship to Drug	Comment
Related	There is clear evidence that the event is related to the use of study drug (e.g., confirmation by positive re-challenge test).
Possible	The event cannot be explained by the patient's medical condition, concomitant therapy, or other causes, and there is a plausible temporal relationship between the event and study drug administration.
Unlikely/Remote	An event for which an alternative explanation is more likely (e.g., concomitant medications or ongoing medical conditions) or the temporal relationship to study drug administration and/or exposure suggests that a causal relationship is unlikely (For reporting purposes, Unlikely/Remote will be grouped together with Not Related).
Not Related	The event can be readily explained by the patient's underlying medical condition, concomitant therapy, or other causes, and therefore, the Investigator believes no relationship exists between the event and study drug.

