## 17. Appendices

### 17.1 Appendix 1: Sampson's Criteria for Anaphylaxis

**ANAPHYLAXIS:** Sampson's definition of anaphylaxis (clinical definition) is the acute onset of illness (minutes to several hours) which involves **SKIN, MUCOSAL TISSUE, or BOTH** (e.g., generalized hives, pruritus or flushing, swollen lips- tongue uvula) **with 1 OR more of the following (Sampson, 2006):**

- **RESPIRATORY:** Airway compromise (e.g., dyspnea, wheeze, or bronchospasm, stridor, reduced PEF, hypoxemia)
- **CIRCULATORY:** Reduced blood pressure or associated symptoms of end-organ dysfunction (e.g., hypotonia, syncope)

**OR**

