7.10 Safety Analyses

7.10.1 Adverse Events

Safety assessments will be based mainly on the nature, frequency, relationship, and severity of adverse events (AEs). AEs will be coded by primary system organ class (SOC) and preferred term (PT) according to the Medical Dictionary for Regulatory Activities (MedDRA) version 21.0. The treatment-emergent adverse events (TEAEs) will be summarized by the number and percentage (n and %) of subjects in each SOC and PT. For summaries by relationship to study drug, “possibly related” will be combined with “related”, and “unlikely/remote related” will be combined with “not related.” When multiple AEs are reported with the same preferred term, the AE of the strongest relation will be included in the summary by relationship, and the AE of the most severe grade will be included in the summary by severity table.

The following AE incidence tables will be presented.

- Overview of TEAEs to include
 - Number (%) of subjects who reported at least one TEAE
 - Number (%) of subjects who reported at least one treatment-related TEAE
 - Number (%) of subjects who reported at least one severe TEAE
 - Number (%) of subjects who reported at least one serious TEAE
 - Number (%) of subjects who reported at least one TEAE leading to treatment discontinuation
- TEAEs by PT sorted by decreasing order of subject incidence in the combined cohort
- TEAEs by SOC and PT sorted alphabetically
- Study Drug-Related TEAEs by SOC and PT
- TEAEs Grade 2+ Severity by SOC and PT

- TESAEs by SOC and PT
- TEAEs leading to study drug discontinuation by SOC and PT

Select TEAEs of pain, tenderness, erythema/redness, induration/swelling, nausea/vomiting, diarrhea, headache, fatigue, and myalgia will be summarized with n and % by toxicity grade.

All AEs will be listed with onset/stop day, relationship to study drug, severity, action taken, and outcome. Pertinent subject information including cohort and demographics will also be included. Separate listings will be provided for TEAEs leading to study discontinuation and Treatment-emergent serious AEs (TESAEs).

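### Table 7 has no valid causality category for a well-timed hives, itch or swelling event that AK002 and urticaria explain about equally, so drug-related TEAEs may be under-reported

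*Protocol*

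**What the plan says.** Protocol 11.3 directs investigators to Table 7, which has four categories:

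- **Related:** requires clear evidence that the drug caused the event; the example given is a positive re-challenge.
- **Possible:** sets two conditions, joined by *and*, with timing judged against dosing: "The event cannot be explained by the patient's medical condition, concomitant therapy, or other causes, and there is a plausible temporal relationship".
- **Unlikely/Remote:** covers either of two situations. One is "An event for which an alternative explanation is more likely (e.g., concomitant medications or ongoing medical conditions"). The other is timing or exposure that argues against a causal link.
- **Not Related:** also has two parts. The first is "The event can be readily explained by the patient's underlying medical condition, concomitant therapy, or other causes". The second, drawn as a consequence of the first, is that "the Investigator believes no relationship exists between the event and study drug".

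For reporting, four categories become two. SAP 7.10.1 states: "possibly related” will be combined with “related”, and “unlikely/remote related” will be combined with “not related". Protocol 13.7.2 has the same rule, and Table 7 itself groups Unlikely/Remote with Not Related. The outputs that use the label are the overview row "Number (%) of subjects who reported at least one treatment-related TEAE" and the table of study drug-related TEAEs by SOC and PT.

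The disease and the reaction share signs. Protocol 2.1 describes chronic urticaria as itchy wheals and flares, with angioedema in some patients. Protocol 8.3.6 gives itching and localized rash as examples of mild to moderate reactions. Appendix 1 counts "generalized hives, pruritus or flushing" and swelling of the lips, tongue or uvula among the signs of anaphylaxis.

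**The concern.** The condition that defines Possible asks the investigator to rule out the patient's own disease. In many indications that is workable. Here the disease consists of the skin signs that an infusion or hypersensitivity reaction would also produce, so the condition is hardest to meet for the reaction type of most interest with an intravenous antibody.

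The trial has one arm, so all-causality counts cannot show an excess of hives over background disease. Attribution therefore leans on the causality label. That label fills the drug-related TEAE outputs. It is also an input to Protocol 12.2, where trial discontinuation refers to possibly or probably related life-threatening or fatal events and to withdrawals for drug-related events, and to the extension stopping rules in Appendix 2.

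**Working it through.** **Step 1. Test one event against each category.** Take hives that start or worsen soon after an infusion, where drug and disease are about equally plausible causes.

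| Category | What it needs | Met? |
|---|---|---|
| Related | Clear evidence | No, unless evidence such as re-challenge exists |
| Possible | Disease cannot explain it, and timing fits | No: timing fits, but the disease can explain it |
| Unlikely/Remote | Alternative more likely, or timing against the drug | No: equally likely, timing fits |
| Not Related | Readily explained otherwise, and investigator believes no relationship | First part arguably yes; second part no, if the drug is suspected |

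No row is satisfied. Table 7 has a gap for events with two comparable causes.

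**Step 2. Follow the event into reporting.** An investigator must still choose. Possible or Related, chosen despite the wording, is reported as related. Either lower category is reported as not related. A blank would count as Related under SAP 6.4, so a missing rating is treated more cautiously than an ambiguous event that was rated.

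**Step 3. See what catches it elsewhere.** Protocol 11.4 makes infusion and hypersensitivity reactions AESIs, recorded whatever the causality. SAP 7.10.1 plans all-causality TEAE tables, full listings, and selected TEAEs by grade, including erythema/redness and induration/swelling. That selection does not name urticaria, itch, angioedema or anaphylaxis, and the SAP's list of AE tables contains no AESI or infusion-reaction table.

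**Step 4. Size.** The plan states no related-event rate, so there is no figure to reproduce. The denominator is 4 cohorts × 12 = 48, which agrees with SAP 3.3 and 3.6.

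A subject whose only drug-related event is put in a lower category removes 1/48 = 2.1 points from the overall rate and 1/12 = 8.3 points from a cohort rate. A subject with another event rated related removes nothing from the overview row.

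For illustration, let *q* be the share of subjects with a truly drug-related event who are lost in this way. Both *q* and the true rate are assumptions. Reported rate = true rate × (1 − *q*):

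| True rate | q = 0 | q = 0.25 | q = 0.50 | q = 0.75 |
|---|---|---|---|---|
| 6/48 | 12.5% | 9.4% | 6.25% | 3.1% |
| 12/48 | 25.0% | 18.75% | 12.5% | 6.25% |
| 24/48 | 50.0% | 37.5% | 25.0% | 12.5% |

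The chance of seeing at least one related case among 48 is 1 − (1 − *p*(1 − *q*))^48. With an assumed *p* = 5% it is 91.5% at *q* = 0, 70.3% at *q* = 0.5 and 45.3% at *q* = 0.75. If investigators rate such events Possible or Related anyway, *q* = 0 and nothing is lost.

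**The case against.** A reader might infer that Table 7 forces these events into Not Related and that the related-event rate is therefore biased downward. The documents do not support that. Not Related also requires the investigator's belief that no relationship exists, which an investigator who suspects the drug does not hold. Related does not require the disease to be excluded, and repeated infusions could supply re-challenge evidence. That last route is weak here, because recurrent hives in a urticaria patient can again be put down to the disease.

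The plan also has real safeguards. Beyond those in step 3:

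- Protocol 11 keeps anticipated fluctuations that do not worsen out of the AE data.
- Protocol 11.6.1 prefers a diagnosis to signs, so peri-infusion hives may be recorded as an infusion reaction.
- Protocol 11.7 judges suspected anaphylaxis by Appendix 1.
- The mild infusion reactions listed in Protocol 2.8 were mostly not urticaria-like (nausea, headache, dyspnea and others). A subject with hives plus one of these can still count as related.
- For the extension, Appendix 2 leaves relatedness in the stopping rules to the Medical Monitor, so the investigator's label is an input and does not decide the matter.

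All of this stands and limits the consequence. None of it supplies a category for the event in step 1, and none of it corrects the drug-related outputs once a lower category has been chosen.

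**Conclusion.** The gap is real and can be read directly from Table 7: a well-timed event that drug and urticaria explain about equally has no valid category, and both lower categories are reported as not related. For events truly caused by the drug, the gap can only lower the drug-related TEAE outputs and weaken the causality input to the stopping rules.

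This is a risk and not a demonstrated bias. Its size depends on how many such events occur and how investigators rate them, neither of which the documents give. It may be zero. The step 4 figures show scale only. All-causality TEAE tables and AESI recording are unaffected. In a single-arm pilot with no hypothesis tests this does not threaten the primary endpoint, but it is worth correcting because it touches the main safety question and the remedy is cheap.

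**What to change.** 1. **Protocol Table 7.** Redefine Possible as: *plausible temporal relationship, and study drug could have caused the event, whether or not another cause is also possible, provided no other cause is more likely.* The phrase *whether or not* matters. A definition that required a second possible cause would leave out well-timed events with no alternative explanation, which the present wording covers.
2. **Table 7 note.** State that a diagnosis of urticaria alone does not justify Not Related for skin or swelling events that start or worsen during or after an infusion. Apply both changes to the extension, which inherits AE reporting through Appendix 2.
3. **SAP 7.10.1.** Add a table of infusion and hypersensitivity AESIs irrespective of causality, by cohort and overall.
4. **Protocol 12.2 and Appendix 2.** The stopping rules refer to a probable relationship, a category that Table 7 does not have. These passages must be reconciled.

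**Cost.** Protocol, CRF-guideline and SAP wording, and one extra table. The reported related rate will be somewhat higher and will include some coincidental flares. The SAP (3.1, 5.1, 7.7.1) distinguishes subjects enrolled under Amendment 2.1 from later ones, so some events will already have been rated. Those should be re-rated under the new definition or flagged, so that two definitions are not mixed in one small dataset.

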### 11.4 Adverse Events of Special Interest

Selected non-serious and serious adverse events that meet criteria for classification as an Adverse Event of Special Interest (AESI) must be recorded in the eCRF, regardless of the Investigator's assessment of relationship to the study drug. Beginning from the time of first study drug infusion and ending at Day 197 or the ET Visit (unless directed otherwise by Allakos), any

new AESI (or new information related to a previously reported AESI) must be recorded in the AE eCRF and designated as an “adverse event of special interest”. Information regarding date of event onset, event severity grading, action taken in response to event, investigator assessment of relationship to study drug, investigator assessment of seriousness, relevant laboratory, pathology, or radiology assessments, event outcome, and date of event resolution will be collected. The Medical Monitor will review data relating to safety during the study, including following the occurrence of AESIs to determine if specific action needs to be taken. The Medical Monitor may also request additional information (not described above) be provided.

Adverse Events of Special Interest for this trial include:

- Malignancies confirmed by histopathological report
- Parasitic infections confirmed by positive clinical laboratory test
- Opportunistic infections (infections known to be more severe or occur more frequently in immunosuppressed populations) as confirmed by positive clinical laboratory test
- Infusion and hypersensitivity reactions, including anaphylaxis.

An AESI that also qualifies as a SAE must also be reported as a SAE. AESIs that are also SAEs must be recorded in the AE eCRF and designated as both “serious” and as an “adverse event of special interest.”

**Note:** If an IRR causes the infusion to be interrupted or slowed, a blood sample (approximately 5 mL serum and 5 mL plasma) must be collected within approximately 1–2 hours from the onset of symptoms for Exploratory Safety Analysis.

## 11.5 Serious Adverse Events

Serious adverse events will be recorded beginning with the signing of the informed consent form and ending at the end of the follow-up period or the Early Termination Visit unless directed otherwise by Allakos. SAE collection in the period after signing the informed consent and before the first study drug infusion will be limited to SAEs that are related to Screening activities. All SAEs will be collected starting at the time of the first infusion of study drug.

An SAE is defined as any AE occurring at any dose that results in any of the following outcomes:

- Death
- A life-threatening AE; the patient is at risk of death at the time of the event. It does not refer to an event that hypothetically might cause death if it were more severe.

- Inpatient hospitalization or prolongation of existing hospitalization
- A persistent or significant disability/incapacity
- A congenital anomaly/birth defect

Other important medical events may also be considered an SAE when, based on appropriate medical judgment, they jeopardize the patient or require intervention to prevent one of the outcomes listed.

**Note:** Medical and scientific judgment should be exercised in deciding whether SAE reporting is also appropriate in situations other than those listed above. For example, important medical events may not be immediately life-threatening or result in death or hospitalization but may jeopardize the patient or may require intervention to prevent one of the outcomes listed in the definition above (including suspected transmission of an infectious agent by a medicinal product should be reported as an SAE). Any AE is considered an SAE if it is associated with clinical signs or symptoms judged by the Investigator to have a significant clinical impact.

Inpatient hospitalization for the purpose of study drug infusion will not be reported as a serious adverse event in this trial.

## 11.6 Adverse Event Reporting Procedures

### 11.6.1 All Adverse Events

Any clinically significant adverse event that is ongoing at the time of study completion or early termination will be followed by the investigator until event resolution, the adverse event is otherwise explained or not considered clinically significant by the investigator.

Abnormal laboratory values or test results constitute adverse events only if they induce clinical signs or symptoms or require therapy.

All AEs identified, whether serious or non-serious, will be recorded in the eCRF until Day 197 or Early Termination.

All AEs, regardless of seriousness, severity, or presumed relationship to investigational product, must be recorded using medical terminology in the source document and the eCRF. Whenever possible, diagnoses should be given when signs and symptoms are due to a common etiology (e.g., dysuria, urinary nitrites should be reported as a urinary tract infection). The Investigator must record in the eCRF his or her opinions concerning the relationship of the AEs to the study drug.

Subjects (or their designees, if appropriate) must be provided with a “study card” indicating the name of the investigational product, the study number, the Investigator’s name, and a 24-hour emergency contact number, and excluded concomitant medications.

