## 9.4 Withdrawal of Subjects from Study

Participation of a patient will be discontinued in the event that:

- An AE or SAE that, in the judgment of the Investigator, requires withdrawal due to its nature, severity, or required treatment, regardless of the causal relationship to treatment
- Major protocol deviations as determined by the Medical Monitor, including significant non-compliance, or loss to follow-up
- Occurrence of an exclusion criterion which is clinically relevant and affects the patient's safety or integrity of the study data, if discontinuation is considered necessary by the Investigator and/or Medical Monitor
- Serum transaminases (ALT and/or AST)  $>3 \times$  ULN AND total bilirubin  $>2 \times$  ULN (confirmed by repeat testing) without an alternative explanation
- Elevation of ALT or AST  $>3 \times$  ULN (confirmed by repeat testing) with the appearance or worsening of symptoms felt by the Investigator to be potentially related to hepatic inflammation, such as fatigue, nausea, vomiting, right upper quadrant pain or tenderness, fever, rash, or eosinophilia
- Use of a non-permitted concomitant drugs and treatments, as defined in Section 8.3.10 as determined by the Medical Monitor.
- Withdrawal of the patient's consent
- Participation in any other trial during the duration of this trial as determined by the Medical Monitor.
- Loss of ability to freely provide consent through imprisonment or involuntarily incarceration for treatment of either a psychiatric or physical (e.g., infectious disease) illness
- Lack of efficacy
- Study terminated by sponsor
- Discretion of the Investigator

If a patient is withdrawn from treatment due to an AE, the patient will be followed and treated by the Investigator until resolved or stable.

Reasonable attempts will be made by the Investigator to provide reasons for patient withdrawals. The reason for the patient's withdrawal from the study will be specified in the patient's source documents.

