## **11. Adverse Event Reporting**

All adverse events will be collected starting from the time of first AK002 infusion and until the end of the follow-up period or the Early Termination Visit, unless directed otherwise by Allakos.

In accordance with 21 Code of Federal Regulation (CFR) 312.32(b) and International Conference on Harmonisation (ICH) Guidance E2A, an AE is any untoward medical occurrence in a clinical investigation of a patient administered a pharmaceutical product and that does not necessarily have a causal relationship with the treatment. An AE is therefore any unfavorable and unintended sign (including an abnormal laboratory finding), symptom or disease temporally associated with the administration of an investigational product, whether or not related to that investigational product. An unexpected AE is one of a type not identified in nature, severity, or

frequency in the current Investigator's Brochure or of greater severity or frequency than expected based on the information in the Investigator's Brochure.

Events that do not meet the definition of an AE include:

- Medical or surgical procedure (e.g., endoscopy, appendectomy); the condition that leads to the procedure is an AE.
- Situations where an untoward medical occurrence did not occur (e.g., social and/or convenience admission to a hospital).
- Anticipated day-to-day fluctuations of pre-existing disease(s) or condition(s) present or detected prior to first study drug infusion that do not worsen.
- Significant reductions in numbers of eosinophils or basophils in blood count, as these are expected therapeutic effects of the study drug.

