### 12.2 General Safety Monitoring

The Investigators and Medical Monitor will review data relating to safety and to conduct of the study.

The trial must be discontinued prematurely in the event of any of the following:

- A life-threatening AE that is possibly or probably related to treatment
- A fatal AE that is possibly or probably related to treatment

- New information leading to unfavorable risk-benefit judgment of the study drug, e.g., occurrence of significant previously unknown adverse reactions or unexpectedly high intensity or incidence of known adverse reactions, or other unfavorable safety findings
- >50% of subjects at any time have been withdrawn due to drug-related AEs, including those related to abnormal laboratory results, or other safety findings
- Sponsor's decision that continuation of the trial is unjustifiable for medical or ethical reasons
- Poor enrollment of subjects making completion of the trial within an acceptable time frame unlikely
- Discontinuation of development of the Sponsor's study drug

Health Authorities and IECs will be informed about the discontinuation of the trial in accordance with applicable regulations. The trial may be terminated or suspended upon request of Health Authorities.

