### **13.7.2 Safety**

Safety assessments will be based mainly on the nature, frequency, relationship, and severity of adverse events (AEs). AEs will be coded by primary system organ class (SOC) and preferred term (PT) according to the Medical Dictionary for Regulatory Activities (MedDRA). The treatment-emergent adverse events (TEAEs) will be summarized by the number and percentage of subjects in each SOC and PT. For summaries by relationship to study drug, “possibly related” will be combined with “related”, and “unlikely/remotely related” will be combined with “not related.” When multiple AEs are reported with the same preferred term, the AE of the strongest relation will be included in summary by relationship, and the AE of the most severe grade will be included in the summary by severity table.

All AEs will be listed with onset/stop day, relationship to study drug, severity, action taken, and outcome. Pertinent subject information including cohort and demographics will also be included. Separate listings will be provided for TEAEs leading to study discontinuation and Treatment-emergent serious AEs (TESAEs).

Laboratory data will be summarized by presenting summary statistics of raw data and change from baseline values (means, medians, standard deviations, ranges) and by presenting number and percentage of subjects with notable laboratory abnormalities.

Data from other tests (vital signs) will be listed, notable values will be flagged, and any other information collected will be listed as appropriate.

All safety and tolerability endpoints will be summarized. Baseline for all safety endpoints will be defined as the last recorded observation before the administration of AK002.

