7.10.2 Laboratory Test

Laboratory data will be summarized by presenting summary statistics of raw data and change from baseline values (means, medians, standard deviations, ranges) at each visit for sample collection. For quantitative laboratory parameters, both actual values and change from baseline values will be summarized.

Shift tables will be presented, in which, lab test results at baseline and post-baseline will be classified into below (<LLN), within (\geq LLN and \leq ULN), and above ($>$ ULN) normal ranges. Subject incidences (n and %) will be presented for the shift from baseline to the post-baseline visits.

Note the summary and shift tables will only use the planned/scheduled tests. However, both scheduled and unscheduled/repeat tests will be included in the data listing.

A complete laboratory data listing, including hematology, biochemistry, urinalysis, and anti-drug antibodies will be provided for all subjects.

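### Protocol Sections 11 and 11.6.1 disagree on whether a symptom-free laboratory abnormality is an AE, and no SAP table described counts subjects who reach the Section 9.4 liver limits

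*Protocol*

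**What the plan says.** Two passages of the protocol decide whether a laboratory value is an AE. Section 11 defines an AE as "any unfavorable and unintended sign (including an abnormal laboratory finding), symptom or disease temporally" associated with giving the product, with no requirement for symptoms or treatment. Section 11.6.1 is narrower: "Abnormal laboratory values or test results constitute adverse events only if they induce clinical signs or symptoms or require therapy". Section 12.2 leans towards the wider reading, since one of its grounds for stopping the trial is that ">50% of subjects at any time have been withdrawn due to drug-related AEs, including those related to abnormal laboratory results". That bullet then goes on to include other safety findings.

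Section 9.4 ends participation under two liver criteria. The first is ALT and/or AST above 3 x ULN together with total bilirubin above 2 x ULN, "confirmed by repeat testing) without an alternative explanation"; it has no symptom condition. The second is ALT or AST above 3 x ULN with new or worsening symptoms. On follow-up, Section 9.4 says: "If a patient is withdrawn from treatment due to an AE, the patient will be followed and treated by the Investigator until resolved or stable". The follow-up rule in 11.6.1 likewise concerns clinically significant adverse events.

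For reporting, Protocol 13.7.2 plans to summarize laboratory data in part "by presenting number and percentage of subjects with notable laboratory abnormalities". SAP 7.10.2 has by-visit descriptive statistics (including ranges) and a shift table with three levels: below, within and above the normal range. It adds: "Note the summary and shift tables will only use the planned/scheduled tests". Unscheduled and repeat tests go to the listing. SAP 3.7 reports no changes to the analyses planned in the protocol. Under Protocol Section 13 and SAP Section 1, the SAP prevails where the two differ.

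**The concern.** The protocol gives confirmed, combined transaminase and bilirubin elevation its own withdrawal rule. Whether such a withdrawal is also an AE depends on which of two conflicting sentences a site follows, so two sites could record the same event differently. Both documents say that safety will be judged mainly on AEs, so the choice affects the headline tables, including the table of TEAEs leading to study drug discontinuation. It also affects follow-up, because the provisions for follow-up to resolution are worded for AEs.

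A table of notable laboratory abnormalities would have been a backstop, catching the subject whatever the AE form said. The protocol planned one and the SAP does not carry it over. A study report could then state that there were no hepatic AEs although a subject had been withdrawn on the liver criterion. The same rules carry into extended dosing: Appendix 2 keeps the AE reporting procedures, SAP Section 8 keeps essentially the same analysis, and the stated objective of that part is long-term safety and tolerability.

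**Working it through.** No planned figure bears on this point, so the check is a trace of one subject through the documents. The subject has confirmed ALT above 3 x ULN and bilirubin above 2 x ULN, no alternative explanation, no signs or symptoms, and no therapy.

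1. **Withdrawal (Protocol 9.4).** The first liver criterion is met and participation ends. The second criterion requires symptoms, so its cases can satisfy the condition in 11.6.1. The gap is confined to the first criterion.

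2. **AE status (Protocol 11 against 11.6.1).** Under Section 11 the finding is an AE. Under 11.6.1 it is not, because withdrawal is not one of the two triggers. It is hard to read 11.6.1 as a mere refinement. Section 11 lists what is not an AE and specifically exempts falls in eosinophils and basophils. That exemption would be largely unnecessary if symptom-free, untreated laboratory changes were already excluded.

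3. **Other reporting routes (Protocol 11.4, 11.5).** No category of AE of special interest covers liver tests. An SAE is defined as a kind of AE, so the important-medical-event route does not clearly close the gap.

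4. **Follow-up (Protocol 9.1, 9.3, 9.4, 10, 11.6.1).** If there is no AE, the provisions in 9.4 and 11.6.1 do not clearly apply. What remains is the early-termination or 28-day visit and safety contact through 28 days after the last dose. That is limited by time and does not run to resolution.

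5. **AE tables (SAP 7.10.1).** With no AE record, the subject is in none of them.

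6. **Laboratory tables (SAP 7.10.2).** In the shift table, a value just above ULN and a value above 3 x ULN fall in the same cell. By-visit ranges can show a high maximum for ALT and another for bilirubin, but they cannot show that both belong to one subject. The confirming repeat, if unscheduled, enters neither table.

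7. **Disposition (SAP 7.2).** The subject is counted as discontinued with a primary reason. The reasons listed include adverse event, investigator decision and other, with no laboratory category.

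8. **Protocol against SAP.** Protocol 13.7.2 plans n and % of subjects with notable abnormalities; SAP 7.10.2 has no such summary; SAP 3.7 reports no change. These three do not agree.

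Scale, for illustration: 1/48 = 2.1% of the planned trial, and 1/12 = 8.3% of one cohort. These express one hypothetical subject and are not expected rates.

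**The case against.** The strongest reply is that the plan is less blind than the trace suggests, and much of that stands.

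- A reader might infer that the subject is settled as not an AE. The documents do not support this: Section 11 says the opposite of 11.6.1, and 12.2 speaks of AEs related to laboratory results. The defect is an unresolved contradiction.
- A reader might infer that the subject drops out of the 12.2 stopping rule. That does not follow. The bullet goes on to include other safety findings, and 12.2 separately allows stopping on new unfavorable safety information. More than 50% of 48 also means at least 25 subjects (24/48 is exactly 50%), so one subject would rarely decide it.
- A reader might infer that the subject is invisible in the SAP output. By-visit ranges, the disposition table and the complete laboratory listing all remain. With about 48 subjects, a listing can be read line by line.
- Safety blood is scheduled at every visit, including early termination, so a high value may well fall on a scheduled sample. The repeat-test point is a possibility only.
- Notable is not defined in 13.7.2, so the omitted summary was not necessarily a table of liver thresholds.
- The medical monitoring text (Protocol 10.5.1 and 11.8) and the content of SAP Appendices C and D are not in the copy reviewed. Nothing is inferred from their absence.

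This narrows the point but does not remove it. None of these items settles AE status, extends follow-up beyond 28 days without an AE, or counts subjects who met the criterion.

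**Conclusion.** The point holds as a contradiction to be reconciled and an undisclosed omission to be repaired. Sections 11 and 11.6.1 give opposite answers for a symptom-free, untreated subject withdrawn under the first liver criterion. If 11.6.1 is followed, that subject has no AE record and no clear provision for follow-up to resolution. Separately, and whichever sentence governs, SAP 7.10.2 leaves out a planned count without saying so, and no table it describes counts subjects by multiple of ULN or by the joint ALT/AST and bilirubin criterion.

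The consequence for AE records and follow-up rests on three assumptions: that sites apply 11.6.1, that the subject has no signs, symptoms or therapy, and that text not available here does not say otherwise. The documents give no basis for estimating how often this would occur. The effect is on the classification and visibility of a rare but important safety finding. The efficacy analysis is not touched.

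**What to change.** 1. **Protocol 11, 11.6.1 and 9.4.** Reconcile Section 11 with 11.6.1 so that the AE status of a laboratory finding that meets a 9.4 criterion, or that leads to discontinuation, is unambiguous. Reconcile the AE-conditioned follow-up wording in 9.4 and 11.6.1 with the laboratory withdrawal criteria. Which clinical rule applies is for the sponsor to decide.

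2. **SAP 7.10.2.** Restore the notable-abnormality table as n (%) of subjects, by cohort and overall, whose worst post-baseline value, scheduled or unscheduled, exceeds the limits already stated in 9.4: ALT or AST above 3 x ULN, total bilirubin above 2 x ULN, and both together. If the sponsor prefers not to restore it, record the removal in SAP 3.7.

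The cost is a few sentences of wording and one table built from data already collected. The downside is that a few more laboratory AEs may be reported, depending on how the sponsor resolves the first item.
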